MI-SI's focus on resolving current SI makes it a promising addition to the VA suicide prevention strategy. In general, the VA strategy is based on using a suicide risk assessment to identify high-risk Veterans, mandating the use of a Safety Plan to identify warning signs and coping skills that can be used to reduce risk, and using Suicide Prevention Coordinators to oversee the care of high-risk Veterans. However, the VA does not have a treatment component that directly targets the resolution of current SI, which may impact the effectiveness of the services being offered. Veterans whose wish to die is stronger than their wish to live may not be willing to engage in treatments or services that can reduce their risk for suicidal behavior. For example, the Safety Plan is used to help individuals identify warning signs that indicate increased risk (e.g. physical pain or loneliness) and coping skills (e.g., taking a walk or calling someone) that can be used to reduce their risk. Veterans who want to die more than they want to live may not be willing to develop a Safety Plan or use it to address their warning signs. However, Veterans who want to live more than they want to die may be willing to engage in such activities. MI-SI can be used to explore Veterans' ambivalence about living and dying, and enhance their wish to live and engage in life sustaining and enhancing behavior. Theoretically, MI-SI should therefore complement the Safety Plan and the other components of the VA suicide prevention strategy.

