- 7. Drug Use Consequences (15 items): The Inventory of Drug Use Consequences (INDUC)  $^{67}$  is the gold-standard self-report assessment of substance-related consequences in the past 90 days. It has been used with Veterans.  $^{68}$
- 8. Insomnia (7 items): The Insomnia Severity Index (ISI) is a widely used, reliable and valid self-report instrument of sleep difficulty. 
- 9. Anger (5 items): The Lifetime History of Aggression Questionnaire (LHAQ) is a brief, valid, and reliable measure of aggression .
- 10. Treatment Engagement (26 items): Treatment engagement will be measured using the Alcohol and Drug Services, Medication, Medical Services, and Psychological Services sections of the Treatment Services Review (TSR-6) which have been shown to be both reliable and valid. 71 The TSR-6 will be used at baseline and the 1, 3 and 6 month follow-ups to inquire about use of these services. The baseline assessment will be used to compare engagement in psychological and alcohol and drug service use between groups to assess whether it needs to be accounted for in the analyses. Engagement in psychological and alcohol and drug services will also be assessed at each follow-up assessment and used as an exploratory outcome. Treatment engagement will be treated as a dichotomous outcome, and will be defined according to the Substance Abuse and Mental Health Services Administration (SAHMSA) Washington's Circle standards, 72 which have been adopted by VA. 73 For residential patients and inpatients, treatment engagement is defined as attending two outpatient visits in the 30-days after discharge. In Veterans with substance use disorders, this measure of treatment engagement has been found to be associated with treatment outcome 74 and hospitalization in those with a suicide attempt history. 75 In Veterans discharged from psychiatric hospitalization, completing two outpatient sessions in at least two of the six months after discharge has also been found to be associated with suicide. 1
- 11. Suicidal Behavior (18 items): The Colombia Suicide Severity Rating Scale (C-SSRS)  will be used to assess history of suicidal behavior at baseline and at follow-up assessment. It has been mandated for use in medication trials by the FDA. 

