Maintaining Blind Outcome Assessments. In-hospital and post-discharge follow-up assessments will be conducted by research assistants who are blind to condition. The blind will be maintained by having research assistants who are not involved in the baseline and treatment phases of the study conduct the assessment by telephone from the CoE. After each outcome assessment, research assistants will be asked if they thought the participant was assigned to the experimental condition (MI-SI plus TAU), control condition (TAU alone), or don't know which condition the participant was assigned to. They will also be asked how they decided the condition to ensure that the blind was indeed broken and the determination was not due to extraneous information such as positive outcome, which would presumably lead a research assistant to guess the MI-SI plus TAU over TAU alone. If blinding was successful, research assistants will not be able to determine assignment at a better than chance rate. 

Randomization. Prior to randomization, participants will be stratified by SSI scores to increase the probability of balanced assignment, which may decrease the probability of a Type 1 error and increase power.  Stratification will be based on a median split using data from pilot study #1. Participants who score below 24 will be in the lower SSI group, and those who score 24 and above will be in the higher SSI group. A blocked randomization procedure using block sizes of 4 and 6 participants will also be used to assure no significant imbalance between the numbers of participants in each condition at any time, and to protect against guessing condition assignment.  Randomization will occur prior to the start of the trial and the results will be recorded in sealed envelopes. After the baseline assessment, the researcher will choose the next envelope (within the strata and block) to determine the participant's assignment. The researcher will then inform the study therapist that a participant has been randomized to receive MI-SI.

**Treatment Conditions.** Participants will be randomized to MI-SI plus TAU or TAU alone.

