In session 1, clinicians will attempt to proceed through all three phases. In session 2, clinicians will summarize session one and use patients' response to the summary to decide which phase to return to. If patients are in phase 3, clinicians' will help them refine and reinforce their plan. If they are undecided about mental health or substance abuse treatment, clinicians will return to phases 1 or 2 and explore reasons against engaging in treatment, build the motivation to engage in it, and strengthen their commitment to do so. Veterans in the MI-SI condition will also complete one telephone booster MI-SI session (30-50 mins.) within one-month (weeks 3-6) after discharge. Telephone contact within one month after discharge is a component of treatments that have been found to reduce risk for suicidal behavior and will be used to increase the dosage of MI-SI.  Participants will be provided a handout with the scheduled telephone follow-up and therapist contact information. Telephone sessions will consist of an abbreviated MI-SI interview following the strategy of session 2. For telephone sessions, phase 3 will include a review of their mental health and substance abuse treatment and explore alternative or additional treatments if they are called for. All MI-SI sessions will also be recorded for coding.

TAU. All patients that are admitted to the acute psychiatric unit receive standard inpatient treatment that includes medication management, case management, meals and a bed, and milieu therapy consisting of creative and social activities (e.g., crafts, video games, karaoke). Families of Veterans may also receive education concerning the Veteran's problems to create a supportive home environment. Suicidal patients receive additional services. VA mental health clinicians are required to complete a Safety Plan with all suicidal Veterans, and each VAMC has hired a Suicide Prevention Coordinator (SPC) to oversee the care of high-risk patients. The Syracuse VAMC also hired Case Managers to help meet essential living needs of suicidal Veterans. SPCs and Case Managers work collaboratively to help suicidal patients transition from inpatient to outpatient treatment. Chart reviews will provide a detailed description of the components of TAU that each participant receives so that suicide-specific TAU can be described in detail. Suicide-related TAU will be controlled for in analyses if differences are observed between conditions.

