Chart Reviews. Research assistants will review participants' charts at two points during the study. The baseline chart review will take place after the baseline interview. Research assistants will cull treatment data from VA medical records using a protocol that we have used in a previous study. Center staff has received 8 hours of training in the protocol and achieved inter-rater reliability as part of the previous study. The protocol emphasizes suicidality, service engagement in the past year, services received during the visit prior to hospitalization, and risk factors for suicide such as depression and substance use disorders. Follow-up chart reviews will occur in concordance with the 6-month follow-up assessment. The protocol will be an abbreviated version of baseline protocol, with the time period limited to the 6 months following discharge. The chart review will also be used to assess use of VA suicide prevention services including the Safety Plan, SPCs, High-risk List, and case managers so that we can describe TAU components that participants receive. Center research assistants already trained in the chart review protocol that will be used. If additional assistants need training, we will use the existing training protocol, which consists of 8 hours of training in the protocol and reviewing practice charts.

**Research Assistant Training and Supervision.** Research assistants will conduct all assessments and receive detailed training and supervision to ensure standardization.

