### **Analytical Plan**

**Data Preparation.** All data will be screened for missing data, outliers, non-normality, non-linearity, and non-homoscedasticity. A combination of statistics and graphic representations will be used to complete these screens. Specifically, missing values analyses, descriptive analyses, frequencies, scatter plots and histograms will be used. The assumptions underlying the proposed statistical analyses will also be tested, which may lead to data transformations or the use of more appropriate statistics. Additionally, imbalances in important covariates between randomized groups will be tested at baseline, which may lead to the identification of covariates to be included in the analyses. Findings will be used to fine-tune the analytical plan if statistical assumptions are unmet or model fit is poor. All analyses will be based on an intent-to-treat approach, analyzed as randomized, include all available data, use multiple imputation for missing data if appropriate, and use one-tailed tests with p < .05 as the cutoff for statistical significance. The study is not powered to test exploratory hypotheses, and we therefore do not

expect to detect significant differences between groups. If the analyses are reported as part of the primary RCT, we will use a p-value of .01 to define statistical significance.

**Aim 2:** To evaluate whether MI-SI plus TAU results in significant reductions in suicidal ideation (SI) and increases in treatment engagement when compared to TAU alone.

Primary Hypothesis: Participants who receive MI-SI plus TAU will report greater reductions in SI over follow-up than participants who receive TAU alone.

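### The rule to adjust for suicide-related TAU whenever the arms differ can adjust the treatment comparison for a consequence of randomisation

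*Combined protocol and SAP*

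**What the plan says.** The TAU paragraph under General Procedures, Treatment Conditions, ends with a firm instruction: "Suicide-related TAU will be controlled for in analyses if differences are observed between conditions". It sets no threshold for a difference, does not say which analyses it covers, and does not restrict the services to those received before assignment.

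The data come from charts. The Chart Reviews paragraph says the review will be used to "assess use of VA suicide prevention services including the Safety Plan, SPCs, High-risk List, and case managers". The follow-up review, done alongside the 6-month assessment, is an abbreviated version of the baseline one, "with the time period limited to the 6 months following discharge".

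Assignment comes earlier, during the inpatient stay. Under Randomization: "After the baseline assessment, the researcher will choose the next envelope".

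The Analytical Plan (Data Preparation) states: "All analyses will be based on an intent-to-treat approach, analyzed as randomized". Its covariate rule looks only at the starting point: "imbalances in important covariates between randomized groups will be tested at baseline". The Treatment Engagement item under Baseline Assessment follows the same logic: "The baseline assessment will be used to compare engagement in psychological and alcohol and drug service use between groups", to decide whether it must be accounted for. Primary Analysis 1 names no TAU covariate for the primary GLMM, but does not exclude one.

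**The concern.** A service received after randomisation can be changed by the treatment. If it is, an arm difference in that service is part of what assignment did. A rule that adjusts exactly when such a difference appears is triggered by the situation in which adjustment does harm.

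The plan gives reason to expect this. Background and Significance argues, with hedging, that motivation affects willingness to develop and use a Safety Plan: "Veterans who want to live more than they want to die may be willing to engage in such activities". The MI-SI sessions aim to build commitment to treatment in patients who are undecided about it, and Exploratory Analysis 1 includes a test of whether MI-SI changes use of Safety Plan coping strategies. A weaker possible route exists in one arm only: under CPRS Notes, senior unit staff co-sign MI-SI session notes that record suicidal ideation, plan or intent.

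Two errors can follow, in opposite directions. If the services lower SSI, adjustment removes part of the true effect. If sicker patients receive more services, comparing patients with equal service use compares patients of unequal severity, and a benefit can appear where none exists. The rule therefore cannot be defended as conservative.

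**Working it through.** **1. Timing.** Assignment follows the baseline assessment, on about day 2 or 3 of the stay. The follow-up chart review covers discharge to 6 months, so everything it records is post-randomisation. Some inpatient services, such as a Safety Plan completed on day 1, could precede assignment; adjusting for those is unobjectionable. The rule does not separate the two.

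**2. The plan's own power.** Inputs from Power Analysis: SD 8.4, one baseline and three follow-ups, baseline-to-follow-up correlation .50, correlation among follow-ups .70, 45 per arm, one-sided .05, Frison-Pocock change method.

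- Variance factor: (1 + 2×.70)/3 + 1 − 2×.50 = .80
- Effective SD: 8.4×√.80 = 7.513
- Standard error of the arm difference: 7.513×√(2/45) = 1.584
- Power at 4 points: Φ(4/1.584 − 1.645) = Φ(.880) = .81

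For 5, 4 and 3 points this gives .935, .811 and .598 one-sided (plan: .94, .81, .60) and .884, .714 and .474 two-sided (plan: .88, .71, .47). The plan's figures reproduce. They refer to a comparison with no adjustment for TAU.

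**3. What adjustment removes.** Take one binary service with uptake difference d between arms that lowers SSI by b points. The total effect is the direct effect plus b×d, so the adjusted arm coefficient is total − b×d. With a total of 4, d = .20 and b = 5, it is 4 − 5×.20 = 3.0.

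The rule adjusts only when the arms differ, so it was simulated: 8,000 trials per scenario, 45 per arm, within-arm SD 7.51, a two-sided two-proportion z test at p<.05 as trigger, and a one-sided .05 test of the arm effect. Uptake, b and the trigger are assumptions; the documents give none of them.

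| Uptake, TAU vs MI-SI | b | 4 − b×d | Share of trials adjusted | Mean estimate under rule | Power |
|---|---|---|---|---|---|
| 50% vs 50% | 5 | 4.0 | .05 | 3.98 | .808 |
| 90% vs 97% | 5 | 3.65 | .29 | 3.81 | .765 |
| 50% vs 60% | 5 | 3.5 | .14 | 3.85 | .785 |
| 50% vs 70% | 2 | 3.6 | .49 | 3.74 | .744 |
| 50% vs 70% | 5 | 3.0 | .49 | 3.31 | .664 |
| 50% vs 70%, trigger p<.20 | 5 | 3.0 | .76 | 3.08 | .615 |

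Monte Carlo error at power .66 is √(.66×.34/8000) = .005. In the fifth row the mean lies below the simple mixture .49×3.0 + .51×4.0 = 3.5. This is because trials that escape the trigger are those with a small observed uptake difference: 3.0 + .51×5×.12 = 3.31 implies about 12 points on average.

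**4. True null.** Here the service is inert, and severity drives both uptake and outcome. The range runs from a weak link (logit coefficient 0.5, severity-outcome correlation .3) to a strong one (1.0 and .5). MI-SI shifts uptake on the logit scale.

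| Logit shift | One-sided rejection under rule | Spurious benefit (points) |
|---|---|---|
| 0 | .049 to .050 | none |
| 0.5 | .049 to .056 | 0 to 0.1 |
| 1.0 | .064 to .084 | 0.2 to 0.4 |
| 1.5 | .072 to .126 | 0.3 to 0.8 |

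The unadjusted test rejected in .046 to .052 of trials throughout.

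**5. Both directions at one larger shift.** With uptake 30 points higher under MI-SI (1,500 trials per scenario, same trigger), a service worth 4 points gives a mean estimate of 2.9 and power .56 for a true 4. An inert service linked to severity (latent correlation .5, 4 SSI points per SD) gives 4.9 for a true 4, and about .13 rejection under the null.

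**The case against.** The strongest reply has four parts.

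- *Intent-to-treat is not literally breached.* Adjustment moves nobody between arms and drops nobody. This stands as a matter of wording. What is lost is the total effect of assignment. The adjusted coefficient is a direct effect only if TAU and SSI share no unmeasured cause, and severity is an obvious candidate.
- *The Analytical Plan governs.* It names no TAU covariate and ties covariates to baseline imbalance, so the TAU sentence could be read as subordinate. The scope is indeed ambiguous. But the sentence is an unrestricted instruction, and nothing says which text prevails.
- *Uptake will hardly differ.* Safety Plans are mandatory for suicidal Veterans and every participant has SSI above 2, so completion may be near universal. For that component the 90% versus 97% row is the better guide: 3.8 points and power .77 against .81. Contact with coordinators and case managers is less fixed, and the documents give no rates for it. The 50% versus 70% row can be neither supported nor excluded.
- *The mechanism is only partly documented.* The Background argument concerns willingness, while the charts record service use. Nothing says that staff who co-sign session notes would change provision, and imminent risk must be reported to staff in either arm. That route is speculative, and the conclusion does not depend on it.

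The plan also models a post-randomisation variable elsewhere, the number of MI-SI sessions, but only in follow-up and sensitivity analyses. TAU-adjusted results belong at the same level.

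**Conclusion.** The concern holds. Followed as written, the rule can adjust the arm comparison for services received after randomisation whenever the arms differ on them. That conflicts with the intent-to-treat commitment read as the total effect of assignment, and with the plan's baseline rule for choosing covariates.

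The defect in the text is certain; its consequence is conditional. It requires MI-SI to change these services, and the services to be related to SSI, causally or through shared severity. If MI-SI leaves them unchanged there is no bias. In the main illustrations (trigger p<.05) the loss runs from none to about 0.7 points of a true 4, with power falling from .81 to .66, and type I error lies between .05 and .13. All service inputs are assumed, so these figures show what is possible and do not forecast it. The planned sample size and stated power are unaffected. The rule should be corrected before analysis.

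**What to change.** Amend the sentence rather than delete it. Suggested content: *The primary GLMM and all other between-arm comparisons will use only covariates measured before randomisation. Suicide-related TAU received after randomisation will be summarised by arm and not adjusted for in these analyses. Any TAU-adjusted result will be labelled a sensitivity or exploratory mediation analysis, and the TAU components used will be named.*

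This keeps the baseline-imbalance rule in Data Preparation and still lets readers see whether co-care differed. The cost is one or two sentences of analysis-plan wording. The chart reviews are already planned, so no new data are needed, and power for a 4-point effect stays at .81. If the team wishes to adjust for inpatient services that preceded assignment, the chart abstraction must record which did.

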#### Methods

# **Treatment Setting**

The study will take place on the 18-bed Acute Psychiatric Inpatient unit at the Syracuse VAMC. In 2009, the previous 16-bed unit treated 498 Veterans, approximately 41 a month, and the average length of stay was 9 days.

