**CPRS Notes.** After the informed consent process is completed, researchers will enter a Study Initiation Note into the participants' digital medical record. To ensure that mental health staff is aware of patients' participation, the attending psychiatrist and nurse manager of the unit will be added as a signees. They will also be added to MI-SI session noted which will document whether the individual exhibited suicidal ideation, plan, or intent during the session.

Participant Procedures. The study will consist of three phases. Phase 1, the assessment phase (15 min.), will be conducted on day 2 or 3 of hospitalization to confirm eligibility. Eligible participants will immediately complete the baseline assessment of risk factors and outcome variables (50 min.). Phase 2, the treatment phase, will occur between day 2 or 3 and discharge. Participants will be randomized to MI-SI plus TAU or to TAU alone. The MI-SI plus TAU condition will include one or two sessions of MI-SI (50 mins. each) in addition to TAU. Sessions will be held on consecutive days and recorded using a digital audio recorder, which will be coded for clinician fidelity. Phase 3, the follow-up phase, will take place after discharge. Participants in the MI-SI plus TAU condition will complete 1 booster MI-SI telephone session within 1 month of discharge (30-50 min.). All participants will be contacted by telephone to complete follow-up assessments (50 min.) at 1, 3, and 6 months to measure outcome variables and risk factors. Research assistants who are blind to condition will complete follow-up assessments.

Table 3: Complete List of Measures

			Time of Assessment			
Domain	Measure	Purpose	Screen	Baseline	*Follow-ups	**Follow- ups after discharge
Demographics	UAB	Screen				
Veteran Status	UAB	Screen				
Psychotic Disorders	MINI	Screen				
Manic Episode	MINI	Screen				
Cognitive Deficits	MMSE	Screen				
ТВІ	TBI-ID	Screen				
Suicidal Ideation (SI)	SSI	Outcome				
Depression	PHQ-9	Risk Factor				
PTSD	PCL-C	Risk Factor		$\sqrt{}$		
Anxiety	BAI	Risk Factor		$\sqrt{}$		$\sqrt{}$
Alcohol Use	AUDIT	Risk Factor		$\sqrt{}$		$\sqrt{}$
Drug Use	DAST-10	Risk Factor		$\sqrt{}$		
Substance Use	SUF	Risk Factor		$\sqrt{}$		$\checkmark$
Frequency						
Substance Problems	InDUC	Risk Factor		V		V
Insomnia	ISI	Risk Factor		V		$\sqrt{}$
Anger	LHA	Risk Factor		V		
Suicidal Behavior	C-CSSRS	Risk Factor		V		V
Contemplation Ladders	CL	Risk Factor		√	$\sqrt{}$	$\sqrt{}$
Treatment Engagement	TSR	Outcome		√		$\sqrt{}$

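### The rule to adjust for suicide-related usual care if the arms differ is not limited to care before randomisation and does not exempt the primary model

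*Combined protocol and SAP*

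**What the plan says.** The description of the comparator (Methods, Treatment Conditions, TAU) ends with this rule: "Suicide-related TAU will be controlled for in analyses if differences are observed between conditions". It does not say which analyses, which period of care, or how a difference is to be judged.

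The same paragraph describes care that runs past the inpatient stay: "SPCs and Case Managers work collaboratively to help suicidal patients transition from inpatient to outpatient treatment". Under Chart Reviews, chart data are "used to assess use of VA suicide prevention services including the Safety Plan, SPCs, High-risk List, and case managers", and the follow-up review is done "with the time period limited to the 6 months following discharge".

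On timing, the screening phase "will be conducted on day 2 or 3 of hospitalization to confirm eligibility", and eligible participants go straight on to the baseline assessment. Under Randomization, "After the baseline assessment, the researcher will choose the next envelope". Under Treatment Setting, "the average length of stay was 9 days".

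The Analytical Plan (Data Preparation) has a separate covariate rule that concerns imbalance at baseline, and it commits all analyses to intent-to-treat. Primary Analysis 1 is an over-dispersed Poisson mixed model for the SSI at 1, 3 and 6 months. It lists no covariates.

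**The concern.** A covariate measured after randomisation can itself be affected by treatment. If MI-SI changes how much suicide-specific care a Veteran receives, holding that care fixed changes the question. The model then estimates the effect of MI-SI with part of its consequences removed, not the total effect promised by the intent-to-treat commitment.

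Two distortions are possible. If the additional care lowers suicidal ideation, adjusting for it removes part of a real benefit. If sicker patients attract more care, adjusting makes the arms non-comparable on severity and can create an effect where none exists.

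The protocol gives reasons to expect some influence. Background and Significance says that Veterans whose wish to die is the stronger "may not be willing to engage in treatments or services that can reduce their risk for suicidal behavior", and it expects MI-SI to work alongside the Safety Plan and the other VA components. Session 2 and the booster call also address taking up treatment. The engagement analysis is exposed in the same way, because its outcome is itself use of services.

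**Working it through.** **1. Is the covariate post-randomisation?** Randomisation follows the baseline assessment on hospital day 2 or 3. With a mean stay of 9 days, 9 − 3 = 6 to 9 − 2 = 7 inpatient days remain on average. Transition work and the 6-month post-discharge period follow. At least part of the charted care therefore comes after assignment.

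**2. Does any other text narrow the rule?** The Baseline Assessment section, the treatment-engagement (TSR-6) item and Data Preparation each tie their own covariate rules to baseline. None refers to suicide-related TAU or withdraws the rule on it. Primary Analysis 1 exempts nothing.

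**3. Reproduce the plan's power figures.** Inputs from Power Analysis: SD 8.4, baseline–follow-up correlation .50, correlation between follow-ups .70, one baseline and three follow-ups, 45 per arm.

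- SD of change = 8.4 × √[(1 + 2 × .70)/3 + 1 − 2 × .50] = 8.4 × √0.80 = 7.51.
- Power for 5, 4 and 3 points: one-sided .935, .811, .598; two-sided .884, .714, .474. All six stated values reproduce.

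**4. Shift at the point where the rule would trigger.** Three things here are assumed: a two-sided p<.05 comparison of TAU between arms, TAU treated as one continuous score, and |r| of 0.1 to 0.4 between TAU and SSI change within arm. The linear scale approximates the planned Poisson model.

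- Trigger gap in SD units = t(.975, 2n − 2) × √(2/n), which is 0.419 for n = 45 and 0.375 for n = 56 (charts available for all 112).
- Shift = trigger gap × 7.51 × |r|, which is about 3.15 × |r| or 2.81 × |r|.

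| \|r\| | 45 per arm | 56 per arm |
|---|---|---|
| 0.1 | 0.31 | 0.28 |
| 0.2 | 0.63 | 0.56 |
| 0.3 | 0.94 | 0.84 |
| 0.4 | 1.26 | 1.13 |

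Against 4 points this is 8% to 31% at 45 per arm and 7% to 28% at 56 per arm.

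**5. Average shift when adjustment is made only if triggered** (40,000 simulated trials per cell, same assumptions; ranges are for |r| of 0.1 to 0.4).

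| True TAU gap | 45 per arm: triggers | 45 per arm: mean shift | 56 per arm: triggers | 56 per arm: mean shift |
|---|---|---|---|---|
| 0 SD | 5% | 0.00 | 5% | 0.00 |
| 0.25 SD | 22% | 0.09 to 0.35 | 26% | 0.09 to 0.37 |
| 0.5 SD | 65% | 0.30 to 1.21 | 75% | 0.32 to 1.30 |

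**6. Direction.** Suppose MI-SI raises care by d SD, each SD of care changes the SSI by b points, and unmeasured severity correlates 0.5 with care and adds u points per SD to the SSI. The adjusted effect is then the total effect − d × (b + 0.5u).

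- True effect −4, u = 0: with d = 0.25 and b = −2 it is −4 + 0.5 = −3.5; with d = 0.5 and b = −4 it is −4 + 2 = −2.0.
- True effect 0: with d = 0.5, b = 0 and u = 4 it is −1.0 (a spurious benefit); with d = 0.5, b = −2 and u = 2 it is +0.5 (a spurious harm).

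**7. Yes/no services.** At 45 per arm a two-sided z-test at .05 first triggers, from 22/45, at 32/45 (z = 2.15), a gap of 22 percentage points. A service already received by 42/45 on TAU cannot trigger upward, because 45/45 against 42/45 gives z = 1.76.

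**The case against.** The strongest reply is that the sentence sits in the description of the comparator, while the analysis text points the other way: intent-to-treat throughout, covariates chosen on baseline imbalance, no TAU term in the primary model, and chart abstraction justified as a way of describing TAU. On that reading this is loose wording, not a planned biased analysis. That stands in part, because using the rule in the primary model is a permitted reading and not a stated commitment. But the sentence says the adjustment will be made, and nothing overrides it.

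The mechanism is also thinner for some services than for others. The protocol's worked example of MI-SI changing behaviour is the Safety Plan, which is required for all suicidal Veterans and may be near ceiling. No passage says that MI-SI alters coordinator contact, case management or High-risk List status. The chart notes from MI-SI sessions are weak evidence, since risk disclosure to staff is allowed in both arms. This is fair: a difference in care is plausible but not shown.

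The magnitudes depend on the assumed trigger. With p<.20 in place of p<.05, the rule fires in about 46% of trials at a 0.25 SD gap, with mean shifts of 0.15 to 0.58. The 9-day stay is a 2009 whole-unit average, and some pilot patients left before the first session, so inpatient exposure may be shorter. The 6 months after discharge are unaffected by that.

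A sponsor could add that the rule guards against unequal co-intervention. Conditioning on care received after assignment does not do this reliably, for the reason in step 6.

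**Conclusion.** The concern holds as a conditional design point, with medium confidence. As written, the rule allows the primary and engagement models to condition on care that follows randomisation and that MI-SI may change. That would undercut the intent-to-treat comparison.

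No stated number in the plan is wrong. The size and direction of any bias cannot be read from the documents. Under the stated assumptions it runs from zero, if MI-SI leaves this care unchanged, to about 1.2 to 1.3 points on average at a 0.5 SD gap and |r| = 0.4. The point does not depend on TAU actually differing. As things stand, the covariates in the main model could be settled by an undefined comparison of data gathered after assignment. The plan should be changed.

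**What to change.** Replace the sentence in the TAU paragraph with: *Suicide-related TAU received after randomisation will be reported by arm and will not be a covariate in the primary or treatment-engagement analyses; any TAU-adjusted model is an exploratory sensitivity analysis.*

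This leaves adjustment for care received before randomisation open. The chart review already collects these services, so no new data are needed. Session notes, the chart-review protocol and safety procedures stay as they are. Sample size and stated power do not change. The only cost is that a TAU-adjusted estimate can no longer serve as a main result; it remains available as a sensitivity analysis.
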